6.3.1 Missing/Incomplete AE Start Date

AE start dates will be imputed as the minimum of the following:

- Initial imputed date, where target date = Treatment start date
- Complete end date

6.3.2 Missing/Incomplete Medication Start Date

Medication start dates will be imputed as the minimum of the following:

- Initial imputed date, where target date = Treatment start date -1
- Complete end date

6.3.3 Missing/Incomplete AE/Medication End Date

AE and medication end dates will be imputed as the minimum of the following:

- Initial imputed date, where target date = Last dose date + 30
- Death date

6.4 Safety Endpoint Conventions

6.4.1 Adverse Events

6.4.1.1 Missing Intensity or Relationship

If the investigator is unable to provide the actual values, the following imputations will be applied:

Table 6-8 Missing AE Intensity and Relationship Imputation Algorithms

Missing Value	Imputation	Timing		
Intensity	Mild	Screening Period		
	Severe	Treatment Period		
Relationship		Screening Period		
	Related	Treatment Period		

6.4.2 Clinical Laboratory Assessments

6.4.2.1 Potentially Clinically Significant Criteria

Laboratory assessments values meeting *any* of the following PCS low or PCS high criteria will be identified as PCS in the laboratory data listing:

Table 6-9 Clinical Laboratory PCS Criteria

			PCS Criteria		
Category	Parameter	SI Unit	PCS Low	PCS High	
Chemistry	Albumin	g/L	< 0.9 × LLN	> 1.1 × ULN	
	Alanine aminotransferase	U/L	_	\geq 3.0 × ULN	
	Aspartate aminotransferase	U/L	_	\geq 3.0 × ULN	
	Bilirubin, total	μmol/L	_	> 1.5 × ULN	
	Calcium	mmol/L	$< 0.9 \times LLN$	> 1.1 × ULN	
	Chloride	mmol/L	< 0.9 × LLN	> 1.1 × ULN	
	Creatinine	μmol/L	_	> 1.3 × ULN	
	Glucose, fasting	mmol/L	< 0.8 × LLN	> 1.2 × ULN	
	Glucose, nonfasting	mmol/L	< 0.8 × LLN	> 1.4 × ULN	
	Potassium	mmol/L	< 0.9 × LLN	> 1.1 × ULN	
	Protein, total	g/L	< 0.9 × LLN	> 1.1 × ULN	
	Sodium	mmol/L	< 0.9 × LLN	> 1.1 × ULN	
Hematology	Hematocrit	Ratio	< 0.9 × LLN	> 1.1 × ULN	
	Hemoglobin	g/L	< 0.9 × LLN	> 1.1 × ULN	
	Platelet count	$10^{9}/L$	\leq 0.5 × LLN	≥ 1.5 × ULN	
	Red blood cell count	$10^{12}/L$	< 0.9 × LLN	> 1.1 × ULN	
	White blood cell count	$10^{9}/L$	\leq 0.7 × LLN	≥ 1.5 × ULN	
Urinalysis	pН	_	< 0.9 × LLN	> 1.1 × ULN	
	Specific gravity	_	_	> 1.1 × ULN	

LLN = lower limit of normal value; ULN = upper limit of normal value; normal value provided by laboratory.

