11.6.3 Laboratory Evaluations and Abnormalities

Continuous clinical laboratory analytes will be summarized for *each* safety population by *double-blind* period treatment group, double-blind treatment/*oxybutynin chloride gel* sequence, or *oxybutynin chloride gel* only, *as applicable, and by* analyte and visit using descriptive statistics (mean, 25th percentile, median, 75th percentile, SD, SEM, minimum, maximum, and number of *patients*). Categorical laboratory analytes, classified as normal or abnormal, will be summarized for *each* safety population by DB treatment group *or oxybutynin chloride gel only group as applicable, and* analyte and visit using the number and percentage of *patients* in each category. The denominators for calculating the percentages will be based on the number of *patients* in each treatment group or *oxybutynin chloride gel* only group, *as applicable*, with nonmissing assessments at a particular visit for *each* safety population.

Shifts to values outside of the normal range will be presented as described above by summarizing the number and percentage of *patients* with evaluable shifts. An evaluable shift is one where both the baseline value (screening value) and the *Pre-Amendment 3* Week 14 or *Post-Amendment 3 Week 14 or* ET values are recorded. The denominators for calculating the percentages will be based on the number of *patients* in each treatment group, *double- blind treatment/ oxybutynin chloride gel sequence*, or *oxybutynin chloride gel* only, *as applicable* who have an evaluable shift for a particular analyte. Evaluable shifts to be presented are $N \rightarrow L$, $N \rightarrow H$, $H \rightarrow L$, $H \rightarrow N$, $L \rightarrow H$, and $L \rightarrow N$ for continuous variables and normal \rightarrow abnormal for categorical variables.

All clinical laboratory values, abnormal clinical laboratory values, and clinically significant laboratory values will also be provided in data listings.

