6.2.2 Safety and Other Assessments

The analysis visit windows for safety and other assessment endpoints are defined as follows:

Table 6-4 Safety Analysis Visit Definitions for Pre-Amendment 3

Ana	lysis Phase	Analysis Visit (Derived)	Study Visit (CRF)	Window
		Baseline	Visit 1/ Visit 2	Treatment Day ≤ 1
	riod	Week 1	Visit 3	Treatment Day [2, 11]
	nd Per	Week 2	Visit 4	Treatment Day [12, 21]
nt	-Blir	Week 4	Visit 5	Treatment Day [22, 35]
Treatment	Double-Blind Period	Week 6	Visit 6	Treatment Day [36, X^1] if patients enters open label period; Treatment Day \geq 36 otherwise
		Week 8	Visit 7	Treatment Day [2, 35] of open- label treatment
	Open-Label Period	Week 14	Visit 8/ET	Treatment Day ≥ 36 of open-label treatment

¹ X = First dose date of open label period – first dose date of double blind period + 1.

Table 6-5 Safety Analysis Visit Definitions for Post-Amendment 3 Open-Label Treatment Period

Analysis Phase	Analysis Visit (Derived)	Study Visit (eCRF)	Window
Treatment	Baseline	Visit A/Visit B	Treatment Day ≤ 1
	Week 2	Visit C	Treatment Day [2, 28]
	Week 6	Visit D	Treatment Day [29, 56]
	Week 10	Visit E	Treatment Day [57, 84]
	Week 14	Visit F/ET	Treatment Day ≥ 85

The following general conventions for repeated or unscheduled assessments will apply unless otherwise specified:

- The latest non-missing assessment within any analysis window will be flagged as the analysis value for any summaries by analysis visit
- All postbaseline assessments will be considered for PCS categorization
- All assessments will be included in respective listings

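### The SAP's only PCS criterion for urine specific gravity, above 1.1 × ULN, lies at 1.10 or higher for any ULN of at least 1.000, so the listing flag cannot mark a genuine result

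*SAP*

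**What the plan says.** SAP Section 6.4.2.1 introduces Table 6-9 by stating that laboratory values meeting any "of the following PCS low or PCS high criteria will be identified as PCS in the laboratory data listing". The urinalysis part of the table has two rows, pH and specific gravity. The second reads "Specific gravity _ _ > 1.1 × ULN": no unit, no low criterion, and a high criterion of more than 1.1 times the upper limit of normal. The table footnote says of the limits: "normal value provided by laboratory". Neither document gives a number for the specific gravity limit.

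SAP Section 6.2.2 adds: "All postbaseline assessments will be considered for PCS categorization". Neither document gives another PCS rule for specific gravity or a different scale for it. Specific gravity is part of the laboratory urinalysis panel in Protocol Appendix 2.

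**The concern.** The high criterion is the same 1.1 multiplier that Table 6-9 uses for ten other parameters, among them sodium, albumin and haemoglobin. On scales that start at zero, such as those three, the multiplier sets a margin of 10% beyond the limit. Specific gravity does not start at zero. Pure water is 1.000, and the information lies in the excess above that. Multiplying the whole number by 1.1 therefore adds at least 0.10 to the threshold, which is large against any plausible excess.

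If the threshold cannot be reached, the row looks like a screen but does not work as one. A reader who sees no specific gravity flags in the listing could take that as an observation about the patients, when the formula has fixed the result in advance.

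**Working it through.** **Inputs**

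- Criterion: value > 1.1 × ULN, low side blank (SAP Table 6-9).
- ULN: supplied by the laboratory, with no number in the documents. Assumed here to be 1.020 to 1.040.
- Highest genuine urine value: not in the documents. Assumed here to be between 1.050 and 1.080.
- Water: 1.000, by the definition of specific gravity.

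The SAP states a multiplier but no numeric threshold, so there is no figure of its own to reproduce.

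**Step 1. Threshold and its excess over water**

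Threshold = 1.1 × ULN. Ratio = (threshold − 1.000) / (ULN − 1.000).

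| Assumed ULN | Threshold | Threshold − 1.000 | ULN − 1.000 | Ratio |
|---|---|---|---|---|
| 1.020 | 1.122 | 0.122 | 0.020 | 6.1 |
| 1.025 | 1.1275 | 0.1275 | 0.025 | 5.1 |
| 1.030 | 1.133 | 0.133 | 0.030 | 4.4 |
| 1.035 | 1.1385 | 0.1385 | 0.035 | 4.0 |
| 1.040 | 1.144 | 0.144 | 0.040 | 3.6 |

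To be flagged, a sample needs 3.6 to 6.1 times the excess over water that the ULN itself represents.

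**Step 2. Dependence on the assumed ULN**

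At ULN = 1.000 the threshold is 1.1 × 1.000 = 1.100, and it rises with the ULN. Any ULN of at least 1.000 therefore gives a threshold of at least 1.10.

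**Step 3. The ULN that would be needed for the flag to fire**

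A value m is flagged only if ULN < m / 1.1.

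- m = 1.050: ULN < 1.050 / 1.1 = 0.9545
- m = 1.080: ULN < 1.080 / 1.1 = 0.9818

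Both limits lie below the value for pure water. Across the assumed range of reachable values, no possible ULN lets the flag fire.

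**Step 4. The same multiplier applied to the excess**

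Threshold = 1.000 + 1.1 × (ULN − 1.000). For ULN 1.020, 1.025, 1.030, 1.035 and 1.040 this gives 1.022, 1.0275, 1.033, 1.0385 and 1.044. These values lie just beyond the limit and can be reached.

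**The case against.** The strongest case against the point is that almost nothing depends on this row, and most of that case stands. A reader might infer that abnormal urine concentration would go unseen and that the safety report would reassure falsely. The documents do not support that inference:

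- Protocol Section 11.6.3 states: "All clinical laboratory values, abnormal clinical laboratory values, and clinically significant laboratory values will also be provided in data listings". A value above the laboratory limit therefore still appears as abnormal.
- Protocol Section 9.7.2 has out-of-range values recorded as adverse events when the investigator judges them clinically significant and they represent a change from baseline.
- The SAP uses PCS only as a mark in the listing and plans no PCS incidence table. Table 6-10, which names the parameters for descriptive and shift tables, contains no urinalysis parameter.
- Laboratory urinalysis is scheduled at screening and at Week 14 or early termination; the baseline test is an on-site dipstick to look for infection. That leaves about one scheduled post-baseline laboratory value per patient.
- Neither document names urine concentration as a particular safety concern for this drug or population.

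Three narrower objections also stand. The highest reachable urine value is an assumption and must be labelled as one. A data-entry or unit error could still trigger the flag, so the claim is limited to genuine values. The blank low cell is not an error in itself, because ALT, AST, total bilirubin and creatinine also have no low criterion. It matters here only because the high side does not work either.

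None of this rescues the criterion. The table already uses a dash where no criterion applies, so an entry in the high cell implies that a working screen was meant.

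**Conclusion.** The point holds as a defect in one listing rule. For any ULN of at least 1.000, the specific gravity threshold in Table 6-9 is at least 1.10. With an assumed ULN of 1.020 to 1.040 it is 1.122 to 1.144. Assuming that genuine urine values do not exceed about 1.05 to 1.08, the flag can fire only on a data error, and with the low side blank no genuine specific gravity result can be marked PCS in either direction.

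The conclusion does not depend on which ULN the laboratory supplies. It does depend on urine not being more than 10% denser than water. The consequence is minor: it reaches the PCS mark in the laboratory listing and no efficacy result, safety summary or decision.

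**What to change.** In Table 6-9, restate the criterion on the excess over water, for example (SG − 1.000) > 1.1 × (ULN − 1.000), and have the sponsor confirm the multiplier. Alternatively, delete the row, so that the listing does not imply a screen that cannot operate. A plain rule of > ULN would work but would only repeat the abnormal flag, whereas every other criterion in the table lies beyond the normal limit.

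The cost is one table cell and one line of listing code. If the criterion is rescaled, some values may now be marked PCS. No other analysis changes.

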6.4.2.2 Continuous Descriptives and Shift Table Parameters

The following laboratory parameters will be summarized:

Table 6-10 Clinical Descriptive and Shift Table Parameters

Category	Parameters							
Hematology	Platelet count		RBC Indices:		WBC	WBC count with Differential:		
	RBC count		MCV		Neutrophils			
	Hemoglobin		MCH		Lympl	nocytes		
	Hematocrit		%Reticulocytes		Monocytes			
					Eosinophils			
					Basophils			
Chemistry	BUN	Potassi	ium	AST (SGOT)		Total bilirubin		
	Creatinine	Sodiun	n	ALT (SGPT)		Total protein		
	Glucose [fasting or nonfasting will be indicated]	Calciu	m	Alkaline phosphatase				

SI = Le Système International d'Unités (International System of Units).

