9.7.2 Clinical Laboratory Evaluations

A blood and urine sample for clinical laboratory evaluations (serum chemistries, hematology, and urinalysis) will be collected from all *patients* at Visit 1 and at Visit 8 *Pre-Amendment 3 and at Visit A and at Visit F Post-Amendment 3*. A sample for a urine culture will also be collected at Visit 1 (*Pre-Amendment 3*) or Visit A (Post-Amendment 3). A urine sample for dipstick urinalysis will be collected at Visit 2 (*Pre-Amendment 3*) or Visit B (Post-Amendment 3) to determine if there is any sign of bacterial infection. Urine samples for pregnancy testing will be collected from female patients of childbearing potential at Visits 1, 6, and 8 (*Pre-Amendment 3*) or Visits A, D and F (Post-Amendment 3).

Samples will be collected, processed, stored, and shipped according to the specific instruction for each test. A detailed list of laboratory evaluations is included in Appendix 2.

All out-of-range laboratory values that are considered by the investigator to be clinically significant and represent a change from baseline will be recorded as adverse events.

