Appendix 2 Clinical Laboratory Evaluations

Hematology (performed on whole blood)

Hemoglobin	Mean cell volume
Hematocrit	While blood cell (WBC) & differential
Red blood cell (RBC) count	Platelet count

Chemistry (performed on serum)

Albumin	Glucose
Alanine aminotransferase (ALT)	Lactate dehydrogenase (LDH)
Aspartate aminotransferase (AST)	Total bilirubin
Blood urea nitrogen (BUN)	Total protein
Gamma glutamyl transferase (GGT)	Creatinine
Sodium	Chloride
Potassium	Bicarbonate
Calcium	Phosphorus

Urinalysis (performed on urine)

Ketones	Protein
Specific gravity	Glucose
Potential for hydrogen (pH)	Blood
Appearance	Leukocyte esterase
Bilirubin	Microscopic examination

Other Labs (performed on urine)

Urine culture¹

Urine pregnancy test²

¹ At screening only.

² Urine pregnancy test will only be performed for females of childbearing potential.

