5.1.1.4.3 Clinical Laboratory Assessments

Clinical laboratory assessments will be summarized by treatment group, double-blind treatment/oxybutynin chloride gel sequence, or oxybutynin chloride gel only group, as applicable, and by analyte and visit for each safety population. Study Part is either Pre-Amendment 3 or Post-Amendment 3.

² Study part refers to pre-amendment 3 and post-amendment 3; pre-amendment 3 has both open-label and double-blind periods, post-amendment 3 has only open-label period.

³ AEs with onset more than 30 days after the last dose of study drug are excluded from analysis.

Table 5-17 Clinical Laboratory Summaries

Endpoint	Description	Timing	Methodology
Descriptives	Summary of change from baseline by laboratory	Visit F ¹ for Post-	CFB
	category and parameter in SI units and analysis	Amendment 3 and	descriptives
	visit	Visit 8 for Pre-	
	 Parameters specified in Section 6.4.2.2 	Amendment 3	
Descriptives	Summary of raw values by laboratory category	Visits A and F ¹	Continuous
	and parameter in SI units and analysis visit	for Post-	descriptives
	 Parameters specified in Section 6.4.2.2 	Amendment 3 and	
	-	Visits 1 and 8 for	
		Pre-Amendment 3	
Shift from baseline ²	Summary by laboratory category and parameter	End of Period	Shift analysis
	 Low, normal, and high categories 	within a Study	
	provided by the central laboratory	Part ²	
	• Parameters specified in Section 6.4.2.2		

¹ Pre-Amendment 3 Week 14 or End of Treatment within Pre-Amendment 3; Post-Amendment 3 Week 14 or End of Treatment within Post-Amendment 3

Laboratory assessments values meeting *any* of the PCS low or PCS high criteria specified in Section 6.4.2.1 will be identified as PCS in the laboratory data listing.

5.1.1.4.3.1 Potential Hy's Law

Potential Hy's Law criteria will be summarized by treatment group, double-blind treatment/oxybutynin chloride gel sequence, or oxybutynin chloride gel only group, as applicable, and visit for each open-label safety population as follows:

Table 5-18 Potential Hy's Law Summaries

Endpoint	Description	Timing	Methodology
Potential Hy's Law	Postbaseline assessment of the following	Study Period	Categorical
within 24-hour window	laboratory parameters based on blood draws	within Study Part ¹	descriptives
	collected within a 24-hour period:	, and the second	-
	• ALT or AST $\geq 3 \times ULN$ and		
	• TBL \geq 2 × ULN and		
	• $ALP < 2 \times ULN$		
Potential Hy's Law	Postbaseline assessment of the following	Study Period	Categorical

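### SAP Table 6-10 leaves all urinalysis entries and six chemistry analytes out of the laboratory summaries that Protocol 11.6.3 promises, and its parameter list does not match Protocol Appendix 2

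*SAP*

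**What the plan says.** **Collected.** Protocol 9.7.2 states: "A blood and urine sample for clinical laboratory evaluations (serum chemistries, hematology, and urinalysis) will be collected from all" patients, at the first and last visits (Visits 1 and 8 before Amendment 3, Visits A and F after it). It adds: "A detailed list of laboratory evaluations is included in Appendix 2". That appendix has a hematology panel, a serum chemistry panel and a urinalysis panel.

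**Promised.** Protocol 11.6.3 says that continuous analytes will be summarized by analyte and visit. It continues: "Categorical laboratory analytes, classified as normal or abnormal, will be summarized for" each safety population. It also calls for shifts: among low, normal and high for continuous analytes, and from normal to abnormal for categorical ones. Listings of all values come in addition to these tables. No analyte is excluded.

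**Specified.** SAP 5.1.1.4.3 repeats that summaries are by analyte and visit. However, each of the three rows of Table 5-17 carries the restriction "Parameters specified in Section 6.4.2.2". That section begins "The following laboratory parameters will be summarized", and its Table 6-10 has two categories, hematology and chemistry.

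**Change log.** SAP 5.2 says that departures from the protocol's planned analyses are described in 5.2.2. The log there has no entry on laboratory parameters.

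**The concern.** The protocol promises tables for the whole panel, and the SAP limits every laboratory table to a shorter list without saying so. This is more than missing detail, because Table 5-17 states a rule and the rule removes promised summaries.

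The SAP's own text suggests an oversight. Table 5-2 defines a normal-to-abnormal shift for categorical variables under its shift method. Table 5-17 is the only summary table that names that method, yet no categorical laboratory analyte reaches it. Table 6-9, which sets limits for potentially clinically significant values, has a urinalysis category (pH, specific gravity) and includes albumin and chloride. The SAP therefore expects these data but uses them only to flag values in a listing.

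Safety is a secondary objective, and the patients are children on intermittent catheterization. Urinalysis is the routine laboratory panel closest to the condition under treatment. As the SAP stands, new findings for leukocyte esterase, blood or protein would have no count with a denominator and no shift rate.

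**Working it through.** The documents give no analyte count to reproduce, so the check compares the two lists line by line.

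**Inputs**
- Protocol Appendix 2, hematology (6 entries): hemoglobin, hematocrit, red cell count, mean cell volume, white cells with differential, platelets.
- Protocol Appendix 2, chemistry (16): albumin, ALT, AST, BUN, GGT, sodium, potassium, calcium, glucose, LDH, total bilirubin, total protein, creatinine, chloride, bicarbonate, phosphorus.
- Protocol Appendix 2, urinalysis (10): ketones, specific gravity, pH, appearance, bilirubin, protein, glucose, blood, leukocyte esterase, microscopic examination.
- SAP Table 6-10, hematology (8): platelets, red cell count, hemoglobin, hematocrit, MCV, MCH, % reticulocytes, white cells with differential.
- SAP Table 6-10, chemistry (11): BUN, creatinine, glucose, potassium, sodium, calcium, AST, ALT, ALP, total bilirubin, total protein.

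Urine culture and the pregnancy test, which Appendix 2 lists separately, are not counted.

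**Comparison**

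| Panel | Appendix 2 | Also in Table 6-10 | Not in Table 6-10 |
|---|---|---|---|
| Hematology | 6 | 8 − 2 = 6 | 0 |
| Chemistry | 16 | 11 − 1 = 10 | 6 (albumin, chloride, bicarbonate, phosphorus, GGT, LDH) |
| Urinalysis | 10 | 0 | 10 |
| Total | 32 | 16 | 16 |

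The subtractions remove the Table 6-10 parameters that Appendix 2 does not list: MCH and % reticulocytes in hematology, ALP in chemistry.

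**Share omitted**
- By Appendix 2 line entry: 16 / 32 = 50%.
- With the white cell line expanded to the total count plus the five cell types named in Table 6-10: 32 + 5 = 37 entries, and 16 / 37 = 43%.
- Blood panels only, by line entry: 6 / (6 + 16) = 6 / 22 = 27%.

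**The three unmatched parameters**
- ALP: Protocol 9.7.1.7 and SAP Table 5-18 both use it in the potential Hy's Law criteria, and the protocol expects the three analytes usually to come from one sample. Appendix 2 therefore looks incomplete.
- MCH: it can be calculated from hemoglobin and red cell count, both in Appendix 2.
- % reticulocytes: the documents show only that it is not in the Appendix 2 panel.

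**The case against.** The strongest reply is that little of clinical importance is lost. Protocol 9.7.2 requires out-of-range values that the investigator considers clinically significant and changed from baseline to be recorded as adverse events, and SAP Table 5-16 counts treatment-emergent events. All values are listed, and albumin, chloride, urine pH and specific gravity also carry flags in the listing. That stands, and it limits the gap to tabulation outside the adverse event route. It does not close the gap: the route depends on investigator judgment, a listing gives no rate, and Protocol 11.6.3 promises tables as well as listings.

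A second reply is that the tables could only be descriptive. Full urinalysis is taken at entry and exit. Visit 8 follows eight weeks of open-label gel for everyone who continued, so it offers no concurrent placebo comparison. The post-Amendment 3 part is uncontrolled, with at least 25 patients and about 10 expected to complete 14 weeks. Exclusion criterion EX03 also accepts asymptomatic bacteriuria as compatible with catheterization, so a new leukocyte esterase finding is hard to interpret. All of this stands. It limits what the tables could show, but the promise was for descriptive summaries.

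Third, the heading of 6.4.2.2 refers to continuous parameters, and table layouts sit in a separate specification that is not available here. But the heading also covers shift tables, and the six chemistry analytes, urine pH and specific gravity are continuous in any case. The SAP has no other laboratory summary apart from Hy's Law. The specification might add the rows, but as written the SAP's list excludes them. The table was read from PDF, but nothing in the text suggests a lost urinalysis row.

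**Conclusion.** The inconsistency is real. Table 6-10 omits 16 of the 32 Appendix 2 line entries (all 10 for urinalysis, six for chemistry) from every laboratory summary in Table 5-17, contrary to Protocol 11.6.3 and without an entry in SAP 5.2.2. It also lists three parameters that are outside Appendix 2. This is a safety-reporting gap that should be corrected. It affects no efficacy endpoint or decision rule.

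A reader might infer three stronger things that the documents do not support:
- **That half of the laboratory safety data is lost.** The 50% is a share of line entries. It falls to 43% with the differential expanded and to 27% for the blood panels alone, and the values are still listed.
- **That MCH and % reticulocytes are never measured and would give empty rows.** Absence from Appendix 2 does not show this. ALP is absent too, yet a safety rule needs it, so Appendix 2 cannot be taken as the full list of what is measured.
- **That new urinary findings would go uncounted altogether.** Those meeting the adverse event rule would be counted.

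The verdict assumes that Table 6-10 is complete as printed and that the separate table specification follows the SAP's list.

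**What to change.** Before database lock:

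1. Add the Appendix 2 urinalysis items to Table 6-10: pH and specific gravity as continuous, the others as normal/abnormal with the normal-to-abnormal shift already defined in Table 5-2.
2. Add a row to Table 5-17 for counts and percentages of categorical analytes by visit, and extend its shift row to normal/abnormal. Its present rows cover continuous summaries and low/normal/high shifts only.
3. Add albumin, chloride, bicarbonate, phosphorus, GGT and LDH to the chemistry row.
4. Reconcile MCH, % reticulocytes and ALP between Table 6-10 and Appendix 2 against what the laboratory actually reports. Do not simply delete them. Confirm in particular that ALP is measured, since the Hy's Law criteria cannot be applied without it.
5. Record the change in SAP 5.2.2. If any analyte is left out on purpose, state that there with the reason.

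The cost is an edit to two SAP tables and the log, plus a few more descriptive rows from data already collected. No new assessment or visit is needed.
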